#### 9.1.3 Post-progression tumor biopsy

A post-treatment core needle or excisional biopsy will be obtained at the time of disease progression. The exact timing of this biopsy will be at the discretion of the treating investigator, but must occur at or after the patient reaches PD by RECIST. The site of biopsy will be selected by the treating investigator; cytology specimens and FNA specimens will not be accepted. Cell blocks made from pleural or pericardial fluid are acceptable. At least six cores will be obtained; one fresh sample for single-cell sorting and RNA sequencing, one each for patient-derived cell line and patient-derived xenograft establishment, one core snapfrozen and one core fixed in formalin and embedded in paraffin for subsequent DNA and protein-based studies. An FNA or core sample will be sent for clinical testing to confirm non-small cell histology. Any additional cores will be transported to the MGH Center for Cancer Research at the Charlestown Navy Yard campus.

#### 9.1.4 Analysis of pre-treatment, on-treatment and post-treatment tumor biopsies

Pre-treatment and progression biopsies will be used to establish patient-derived cell lines as has been previously described (Crystal, et al, Science 2015.) Next-generation sequencing will be performed at Novartis. Because the scientific assays used to interrogate tumor specimens are constantly evolving, additional tumor samples may be used for research purposes in exploratory studies. These studies may include DNA sequencing (including gene-specific, whole exome, and whole genome sequencing), RNA sequencing (including RT-PCR, Q-PCR, and whole transcriptome sequencing), DNA methylation studies (including CHIP-sequencing), and proteomics assays. Live tissue may also be cultured in vitro and/or implanted into immunodeficient mice to generate xenograft models. Any exploratory research studies will be performed at the MGH Center for Cancer Research at the Charlestown Navy Yard Campus or at the Novartis Institute for Biomedical Research.

#### 9.2 Longitudinal circulating tumor DNA analyses

Blood samples will be collected for circulating tumor DNA analyses at screening, C1D1, C1D3 (as close to 48 hours after the first dose as possible), C1D8, C1D15 and on the first day of each subsequent cycle (every 28 days) until the end of treatment. Two Streck tubes (a total of 20 cc of blood) will be collected at each time point. Samples will be sent to the Charlestown Navy Yard via US Ground courier for isolation of plasma within 8 hours of sample collection. Plasma will be isolated from each tube according to the protocol in Appendix C. Plasma will be stored frozen at -80 degrees until ctDNA extraction. The remaining whole blood will be used to extract peripheral blood mononuclear cells for germline analyses.

Next-generation sequencing will be used to analyze pre-treatment ctDNA sample and the one obtained at progression to identify mechanisms of resistance to the EGF816/gefitinib combination. The intervening samples will then be studied via ddPCR or next-generation sequencing to further characterize dynamic molecular changes occurring in ctDNA over time. Because the scientific assays used to interrogate ctDNA specimens are constantly evolving, additional samples may be used for research purposes in exploratory studies.

Please Note: [name] ([contact]) should be alerted 24hrs prior to each sample being drawn if possible (or as soon as it is determined that a sample will be drawn). [contact]

Samples Shipped To: MGH Charlestown Navy Yard Facility [name] Laboratory [name]

#### 9.3 Pharmacokinetic studies:

A pre-EGF816 dose blood sample will be obtained at baseline on C1D1 and on C1D15 for pharmacokinetic analysis to establish steady state levels of EGF816 and gefitinib. For each timepoint, at least two 2mL of blood will be collected in a properly labelled plastic lavender top K2-EDTA-tube. Immediately after each tube of blood is drawn, it should be inverted gently

several times to ensure the mixing of tube contents. Avoid prolonged sample contact with the rubber stopper. Place the tube upright in a test tube rack surrounded by ice until centrifugation. Within 30 minutes, centrifuge the sample at between 3-5 degrees Celsius for 10 minutes at approximately 2000g (or centrifuge the sample at room temperature if tubes placed on ice quickly after processing). Immediately after centrifugation, aliquot the collected plasma into two uniquely labeled tubes (PK plasma A and B). The tubes will be frozen immediately over solid carbon dioxide (dry ice) then kept frozen at -70 degrees Celsius or colder pending analysis, which will be performed in collaboration with WuXi AppTec.

Samples will be shipped frozen at -70 to:

[name] [name] [contact] E-mail: [name]

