## 1.4 Exploratory Objectives

- To characterize the pharmacokinetic interactions between gefitinib and EGF816.
- To evaluate resistance mechanisms to EGF816 and gefitinib.
- To characterize the molecular response to treatment in on-treatment tumor biopsies and in circulating tumor DNA.

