In preclinical toxicology studies conducted in rats and dogs, EGF816 was overall well tolerated at plasma concentrations that resulted in anti-tumor activity in rodent efficacy models. One of the off-targets of EGF816 is Tyrosine kinase expressed in hepatocellular carcinoma (TEC) family kinases. The results of a T-cell Dependent Antigen Response (TDAR) assay in rats indicated a trend for a dose-response effect of EGF816 on inhibiting the generation of antigen-specific antibodies to a foreign antigen; this effect was reversible following withdrawal of EGF816. In the first-in-human study of EGF816 in patients with EGFR-T790M NSCLC, preliminary PK data demonstrated that the EGF816 exposure increased largely in proportion to dose 75 mg to 350 mg, quaque die/ daily (q.d.) and the terminal half-life (T1/2) ranged from 13 hours (h) to 18h EGF816 appears to be efficacious at doses of 75 mg q.d. and above, and preliminary exposure-response analyses showed a flat relationship between EGF816 steady state trough concentration and overall response rate (RR). Preliminary population PK analysis indicated similar exposures from the matched doses in capsule and tablet formulations.

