#### 5.3 Agent Administration

#### 5.3.1 EGF816

Investigational Product: EGF816 Pharmaceutical Form: Tablets Source: Novartis Procurement: Provided via sponsor, dispensed from research pharmacy. Unit Strength: 150mg tablets Daily Dose: 100 mg once daily Duration of Use: Continuous daily dosing without interruption Administration Route: Oral (swallowed) Schedule: Once daily, with or without food

Missed Doses/Vomited Doses: If a patient inadvertently does not take the EGF816 dose at their usual time, he or she may take the dose up to 6 hours later; in other words, they may continue as long as it is at least 6 hours before the next dose of gefitinib is due to be taken. The daily treatment schedule will be resumed the next day with the patient taking the scheduled dose at the usual time. If an entire daily dose is skipped, the patient should resume treatment the following day with their regular dose. No "make-up dose" or increased dosing should occur. If a dose is vomited within 1 hour of administration, medications to control nausea and vomiting should be used, and the dose can be repeated. Patients should report all vomited, missed or delayed doses to the study staff and will be provided with a medication diary which should be turned in at every visit (see appendix 5.)

Tablets should be swallowed whole and not chewed or opened. Patients should be instructed to take their dose of each drug at approximately the same time of day. Drugs should be separated by approximately 12 hours (e.g, gefitinib taken in the morning and EGF816 in the evening.) The time of drug administration should be recorded by the patient in the study-provided drug diary. On days when blood for PK samples need to be collected in clinic, the patient should hold their morning gefitinib until arrival, and take the dose in the clinic after clearance to do so from the care team.

Grapefruit or grapefruit juice, seville orange (and juice), pummelos, star citrus fruits and hybrids of these mentioned fruits should be avoided during study treatment.

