## 5.3.2 Gefitinib

Commercial Product: Gefitinib Pharmaceutical Form: Tablets Source: Commercial pharmacy Procurement: Obtained directly from commercial pharmacy, delivered to patient. Unit Strength: 250 mg tablets Daily Dose: 250 mg once daily Duration of Use: Continuous daily dosing without interruption Administration Route: Oral (swallowed) Schedule: Once daily, with or without food

If a patient inadvertently does not take the gefitinib dose at their usual time, he or she may take the dose up to 6 hours later, in other words, they may continue as long as it is at least 6 hours before the next dose of EGF816 is due to be taken. The daily treatment schedule will be resumed the next day with the patient taking the scheduled dose at the usual time. If an entire daily dose is skipped, the patient should resume treatment the following day with their regular dose. No "make-up dose" or increased dosing should occur. If a dose is vomited within 1 hour of administration, medications to control nausea and vomiting should be used, and the dose can be repeated. Patients should report all vomited, missed or delayed doses to the study staff and will be provided with a medication diary which should be turned in at every visit (see appendix 5.)

Tablets should be swallowed whole and not chewed or opened. However, gefitinib may be dissolved in 4-8 oz of water if patients have difficulty swallowing the tablets. **Drugs should be separated by 12 hours (e.g, gefitnib taken in the morning and EGF816 in the evening.)** Patients should be instructed to take their dose of each drug consistently at approximately the same time each day. Time of drug administration should be recorded by

the patient in the study-provided drug diary. On days when blood for PK samples need to be collected, the patient should take the dose in the clinic.

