#### Table 10-1 Study Calendar

\* Re-consent is required if treatment starts more than 28 days after the original consent.

- a. Treatment with EGF816 and gefitinib can be continued beyond progression at the discretion of the treating investigator (see section 5.5)
- b. Sodium, potassium, calcium, magnesium, glucose, creatinine, total bilirubin, alkaline phosphatase [ALP], aspartate transaminase [AST], alanine transaminase [ALT], blood urea nitrogen [BUN], total protein, albumin and lactic dehydrogenase [LDH]. If screening chemistry is drawn > 7 days before C1D1, chemistry should be redrawn on C1D1. These do not need to re-meet eligibility.
- c. Screening labs should include HBsAg, HBsAb, HCV-Ab, and HBcAb. Check HBV-DNA if HBsAg and/or HBcAb are positive (see section 6.1.3). In addition, HBV DNA and/or HCV RNA monitoring will be required for some patients based on initial screening (see section 6.1.3)
- d. Urinalysis should be performed at baseline and then only if clinically indicated.
- e. Radiologic evaluation (CT chest, abdomen and pelvis) should be performed every 8 weeks of treatment. After completing 1 year of treatment, radiologic evaluations should be performed every 12 weeks. Brain imaging (MRI, or CT with contrast in patients with contraindications to MRI) should be obtained every 8 weeks for patients with known brain metastases at the start of treatment. For patients without known baseline brain metastases, CNS imaging should be obtained if clinically indicated based on symptoms.
- f. Pre-treatment core needle or excisional should be done within 28 days of start of treatment
- g. On-treatment biopsy should be performed between D15 and D21 of cycle 1. On the day of the on-treatment biopsy, patients should take both study drugs. Their morning gefitinib dose can be taken with sips of water.
- h. Post-treatment core needle biopsy should be obtained at the time of disease progression. The exact timing of this biopsy will be at the discretion of the treating investigator, but must occur at or after the patient reaches PD by RECIST.
- i. Cycle 1, Day 3 ctDNA blood draw should be performed as close to 48 hours after first dose as possible.
- j. Pre-dose steady state levels of EGF816 and gefitinib will obtained on C1D1 and C1D15.

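### PK draws labelled pre-dose steady state for both drugs are timed to gefitinib only; C1D1 is pre-treatment, and C1D15 EGF816 could be misread as a trough

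*Combined protocol and SAP*

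**What the plan says.** The PK data serve an exploratory objective (section 1.4): "To characterize the pharmacokinetic interactions between gefitinib and EGF816".

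Four places bear on when the sample is taken:

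- Section 9.3, referring to both drugs: "A pre-EGF816 dose blood sample will be obtained at baseline on C1D1 and on C1D15 for pharmacokinetic analysis to establish steady state levels".
- Table 10-1, footnote j: "Pre-dose steady state levels of EGF816 and gefitinib will obtained on C1D1 and C1D15".
- Section 5.3.1, for PK days: "the patient should hold their morning gefitinib until arrival, and take the dose in the clinic after clearance to do so from the care team".
- Section 5.3.2, for gefitinib: "On days when blood for PK samples need to be collected, the patient should take the dose in the clinic".

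On spacing, section 5.3.1 says "Drugs should be separated by approximately 12 hours (e.g, gefitinib taken in the morning and EGF816 in the evening"; section 5.3.2 repeats the 12-hour separation in bold. Section 10 adds that assessments come before any study agent is given.

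The protocol gives no clock time for the draw, no intended time since the last EGF816 dose and no PK-day instruction for EGF816. Section 13 names no PK comparator or method of PK analysis. Sections 5.3.1 and 5.3.2 do have patients record dose times in a diary.

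**The concern.** The labels and the PK-day instructions describe different samples. With the drugs half a day apart, a single draw can fall at the end of the dosing interval for one drug only. Section 9.3 names EGF816 as the drug the sample precedes, while sections 5.3.1 and 5.3.2 organise the day around gefitinib. The steady-state label also covers C1D1, when the regimen has not started.

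The interaction objective is what is at stake. Section 5.4.2 says both drugs are metabolised by CYP3A4, so the question is a reasonable one. Both drugs start together, so the trial has no planned single-agent period and EGF816 must be judged against outside single-agent data. The EGF816 concentration measure that section 2.2.1 names from the first-in-human study is the steady-state trough. An analyst who takes the pre-EGF816 label to mean trough could set a mid-interval level beside a true trough. Sites that follow section 9.3 and sites that follow section 5.3.1 could also draw at different times and report both under one label.

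**Working it through.** The protocol states no expected concentration or PK sample size, so there is no planned figure to reproduce. The check has two parts.

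**1. What each sample is**

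- *C1D1.* Assessments precede any study agent (section 10), so no EGF816 has been taken and the fraction of steady state reached is 0. The same holds for gefitinib as study treatment. One qualification is that section 3.1.5 lets the six run-in patients have had under three months of a prior EGFR TKI, so some gefitinib from before the study cannot be ruled out in them.
- *C1D15, steady state.* Fraction reached = 1 − 2^(−hours/half-life). Nominally 14 × 24 = 336 hours have passed. That is 336/18 = 18.7 to 336/13 = 25.8 half-lives. With the visit window at −3 days, 264/18 = 14.7 half-lives, still over 99.99%. The steady-state label is therefore right for EGF816 at C1D15.
- *C1D15, time since dose.* With gefitinib in the morning and EGF816 the evening before, a morning draw ahead of gefitinib is about 24 hours after gefitinib and about 12 hours after EGF816.

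**2. Size of the difference for EGF816 at C1D15**

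Inputs: once-daily dosing, so a 24-hour interval (section 5.3.1); separation of about 12 hours (sections 5.3.1 and 5.3.2); and, from section 2.2.1, "the terminal half-life (T1/2) ranged from 13 hours (h) to 18h".

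Assuming single-exponential decline after absorption, the level at t hours relative to the 24-hour trough is 2^((24 − t)/half-life).

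| Hours since EGF816 | Half-life 18 h | Half-life 13 h |
|---|---|---|
| 10 | 2^(14/18) = 1.71 | 2^(14/13) = 2.11 |
| 12 | 2^(12/18) = 1.59 | 2^(12/13) = 1.90 |
| 14 | 2^(10/18) = 1.47 | 2^(10/13) = 1.70 |
| 16 | 2^(8/18) = 1.36 | 2^(8/13) = 1.53 |
| 24 | 1.00 | 1.00 |

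At 12 hours with no interaction at all, the level is 59% to 90% above trough. In the other direction, a true fall to 1/1.59 = 0.63 or 1/1.90 = 0.53 of the single-agent level, that is a fall of 37% to 47%, would read as no change.

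Sensitivity to absorption: a one-compartment oral model at steady state has C(t) proportional to e^(−kt)/(1 − e^(−24k)) − e^(−ka·t)/(1 − e^(−24ka)), with k = ln 2/half-life. The absorption rate ka is not in the protocol and is assumed. At 12 hours, ka of 0.5 to 2 per hour gives 1.58 to 1.90, and a slow ka of 0.15 per hour gives 1.39 to 1.57.

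**The case against.** A reader might infer that EGF816 exposure will look raised and that the trial will report a false interaction. The documents do not support that. It would require an uncorrected comparison with a single-agent trough, and no such comparison is planned. Neither section 9.3 nor footnote j uses the word trough for these samples. In section 2.2.1 the trough belongs to an exposure-response analysis in another study, and the same section mentions a population PK analysis, so a time-adjusted reference may be available.

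Other points on that side also stand:

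- A morning draw is literally before that evening's EGF816 dose. With section 10, the text can be read as one draw before either drug that day. The label misleads only if pre-dose is taken to mean trough.
- Section 9.3 already calls C1D1 baseline, so an analyst is unlikely to be badly misled there.
- The morning/evening order is an example, although section 5.3.1 and calendar footnote g both presume a morning gefitinib dose.
- On that order, gefitinib itself is sampled at the end of its interval and is unaffected.
- Dose times are already in the diary.
- PK feeds no primary or secondary endpoint and no run-in decision.

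These points limit the consequence but do not remove the mismatch. Whichever drug is taken first, one draw cannot be end-of-interval for both. The diary holds dose times but not the draw time: section 9.3 does not ask for it, whereas Appendix C does for the ctDNA sample. Without that link, an analysis by time since dose may not be possible afterwards.

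**Conclusion.** The labelling and the PK-day instructions conflict and need reconciling. C1D1 is a pre-treatment sample and cannot be steady state for the regimen. C1D15 is at steady state for EGF816 but, on the example schedule, about mid-interval. Its EGF816 level would be about 1.6 to 1.9 times trough at 12 hours, and roughly 1.4 to 2.1 times for draws between 10 and 16 hours.

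That size rests on the protocol's half-life range (from data it calls preliminary), morning gefitinib with evening EGF816, and single-exponential decline; slow absorption would make it smaller. It applies to EGF816 at C1D15 only. The supported conclusion is that the value could be mistaken for an interaction, or could hide a fall, if it is treated as a trough. This is a minor point on an exploratory objective, worth correcting because draw times that go unrecorded may be unrecoverable.

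**What to change.** - Reconcile sections 5.3.1, 5.3.2, 9.3 and Table 10-1 footnote j so that they agree on when the sample is drawn relative to each drug. No dosing schedule is proposed here.
- Label C1D1 a pre-treatment blank, noting any prior gefitinib in run-in patients, and drop the steady-state label for it.
- Record the clock time of each PK draw and link it to the last dose time of each drug from the diary.
- State in section 13 that EGF816 will be analysed by actual time since dose, against time-matched single-agent values or through a population PK model, and not as a trough.

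The cost is rewording in these places, a short analysis statement, one added recorded time per draw and the link to diary data already collected. No extra samples or visits are needed.

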#### **10. STUDY CALENDAR**

Baseline evaluations are to be conducted within 28 days prior to start of protocol therapy. Scans must be done  $\leq$ 4 weeks prior to the start of therapy. In the event that the participant's condition is deteriorating, laboratory evaluations should be repeated within 48 hours prior to initiation of the next cycle of therapy.

Assessments must be performed prior to administration of any study agent. Study assessments and agents should be administered within  $\pm$  3 days of the protocol-specified date, unless otherwise noted.

able 10-1 Study Calenda	••					1	,	
	Pre- Study	C1D1	C1D3	C1D8	C1D15	C2D1 and D1 of all subsequen t cycles n	Disease Progression	Off Study k
EGF816		X					Xa	
Gefitinib		X					Xa	
Informed consent*	X							
Medical history	X	X		X	X	X		Х
Concurrent meds	X	X		X	X	X	X	Х
Physical exam (including VS, weight)	x	X		X	x	X	Х	Х
Performance status	X	X		X	X	X	X	Х
CBC w/diff	X	X 		X	X	X	X	Х
Serum chemistry b	X	X		X	X	X	X	Х
Hepatitis serologies c	X							
Urinalysis d	X							
ECG	X	X m				X m		
PK Sampling		Xj			Xj			
Adverse event evaluation		Х		X	X	X	Х	
Radiologic evaluation (CT C/A/P, +/- brain imaging) e	x					X		
B-HCG (serum or urine)	x	Х				X		
Tumor biopsy	Xf				X g		X h	
Plasma for ctDNA analysis	х	Х	X i	Х	X	Х	Х	Х

#### Table 10-1 Study Calendar

\* Re-consent is required if treatment starts more than 28 days after the original consent.

- a. Treatment with EGF816 and gefitinib can be continued beyond progression at the discretion of the treating investigator (see section 5.5)
- b. Sodium, potassium, calcium, magnesium, glucose, creatinine, total bilirubin, alkaline phosphatase [ALP], aspartate transaminase [AST], alanine transaminase [ALT], blood urea nitrogen [BUN], total protein, albumin and lactic dehydrogenase [LDH]. If screening chemistry is drawn > 7 days before C1D1, chemistry should be redrawn on C1D1. These do not need to re-meet eligibility.
- c. Screening labs should include HBsAg, HBsAb, HCV-Ab, and HBcAb. Check HBV-DNA if HBsAg and/or HBcAb are positive (see section 6.1.3). In addition, HBV DNA and/or HCV RNA monitoring will be required for some patients based on initial screening (see section 6.1.3)
- d. Urinalysis should be performed at baseline and then only if clinically indicated.
- e. Radiologic evaluation (CT chest, abdomen and pelvis) should be performed every 8 weeks of treatment. After completing 1 year of treatment, radiologic evaluations should be performed every 12 weeks. Brain imaging (MRI, or CT with contrast in patients with contraindications to MRI) should be obtained every 8 weeks for patients with known brain metastases at the start of treatment. For patients without known baseline brain metastases, CNS imaging should be obtained if clinically indicated based on symptoms.
- f. Pre-treatment core needle or excisional should be done within 28 days of start of treatment
- g. On-treatment biopsy should be performed between D15 and D21 of cycle 1. On the day of the on-treatment biopsy, patients should take both study drugs. Their morning gefitinib dose can be taken with sips of water.
- h. Post-treatment core needle biopsy should be obtained at the time of disease progression. The exact timing of this biopsy will be at the discretion of the treating investigator, but must occur at or after the patient reaches PD by RECIST.
- i. Cycle 1, Day 3 ctDNA blood draw should be performed as close to 48 hours after first dose as possible.
- j. Pre-dose steady state levels of EGF816 and gefitinib will obtained on C1D1 and C1D15.
- k. The duration of EGF816 and gefitinib administration will be determined as specified in section 5.5. Follow up for survival will be performed by telephone contact or clinic visits every 3 months (+/-1 month) after exit visit until the participant is deceased or lost to follow up.
- 1. If screening CBC with differental is done > 7 days from C1D1, CBC with differental should be repeated on C1D1. These do not have to remeet eligibility.
- m. ECGs at each cycle visit should be captured pre-dose
- n. After completing 1 year of treatment, visits should be performed every 6 weeks.

